### 12.3.3.1.2 Analysis of Secondary Variables

#### Analysis of Key Secondary Variables

The key secondary efficacy variables include:

- **Absolute change in ppFEV1 through Week 24:** Analysis of this variable will be based on an MMRM model that is exactly the same as the primary efficacy variable. Data obtained from the Day 15, Week 4, Week 8, Week 12, Week 16, and Week 24 Visits will be included in the model, however, the Day 15 Visit will not be included in the estimation of the average treatment effect through Week 24.
- **Number of PEx through Week 24:** Analysis of this variable will be performed using a negative binomial regression model with a fixed effect for treatment, as well as continuous baseline ppFEV1, age at screening (<18 versus ≥18 years of age), and sex (male versus female) as covariates. The logarithm of the subject-specific PEx analysis period duration (defined in the SAP) will be treated as the offset in the model.
- **Absolute change in SwCI from baseline through Week 24:** Analysis of this PD variable will be based on an MMRM model similar to the analysis of the primary efficacy variable. Data obtained from Week 4, Week 8, Week 12, and Week 24 Visits will be included in the model and all of these visits will be included in the estimation of the average treatment effect through Week 24.
- **Absolute change in the CFQ-R respiratory domain score from baseline through Week 24:** Analysis of this domain will be based on an MMRM model similar to the analysis of the primary efficacy variable. Data obtained from Week 4, Week 8, Week 12, Week 16, and Week 24 Visits will be included in the model and all of these visits will be included in the estimation of the average treatment effect through Week 24.
- **Absolute change in BMI from baseline at Week 24:** Analysis of this variable will be based on an MMRM model similar to the analysis of the primary efficacy variables. Data obtained

from Day 15, Week 4, Week 8, Week 12, Week 16, and Week 24 Visits will be included in the model.

- **Absolute change in SwCI from baseline at Week 4:** Analysis of this variable will be based on an MMRM similar to the analysis of the primary efficacy variable. Data obtained from Week 4, Week 8, Week 12, and Week 24 Visits will be included in the model to estimate the treatment effect at Week 4.
- **Absolute change in CFQ-R respiratory domain score from baseline at Week 4:** Analysis of this variable will be based on an MMRM model similar to the analysis of the primary efficacy variable. Data obtained from the Week 4, Week 8, Week 12, and Week 24 Visits will be included in the model to estimate the treatment effect at Week 4.

The key secondary endpoints will be formally tested only during the final analysis when all subjects have completed study participation and the primary endpoint is statistically significant either at the IA or at the final analysis. Additional details will be provided in the SAP.

### **Analysis of Other Secondary Variables**

Other secondary efficacy variables include:

- **Time-to-first PEx through Week 24:** Time-to-first PEx will be analyzed using the Cox regression model. The model will include a fixed effect for treatment, as well as continuous baseline ppFEV1, age at screening (<18 versus ≥18 years of age), and sex (male versus female) as covariates. A subject who does not experience a PEx during the PEx analysis period will be censored at the PEx analysis period end date. If the proportional hazards assumption is violated for any of the categorical covariates, a stratified Cox regression will be conducted. Additionally, the Kaplan-Meier method will be used to produce a graphical presentation of the cumulative exacerbation-free survival rate for each treatment group and to estimate the cumulative exacerbation-free survival rate by treatment group. Note: If the number of events is <5 in either treatment group, Cox regression will not be performed and the analysis of the time-to-first event will be restricted to the Kaplan-Meier method.
- **Absolute change in BMI z-score from baseline at Week 24 (for subjects ≤20 years of age at Baseline):** Analysis of this variable will be based on an MMRM model similar to the analysis of the primary efficacy variable, for subjects ≤20 years of age at Baseline. Data obtained from Day 15, Week 4, Week 8, Week 12, Week 16, and Week 24 Visits will be included in the model.
- **Absolute change in body weight from baseline at Week 24:** Analysis of this variable will be based on an MMRM model similar to the analysis of the primary efficacy variable. Data obtained from Day 15, Week 4, Week 8, Week 12, Week 16, and Week 24 Visits will be included in the model.

Additional details will be provided in the SAP.

### 12.3.3.3 Interim Analysis

#### 12.3.3.3.1 Analysis of Primary Variables

During the IA, the analysis of the primary efficacy variable of absolute change in ppFEV1 from baseline at Week 4 will be performed using an MMRM with change from baseline at Day 15 and Week 4 as the dependent variable. Other details of the model are same as that described for the final analysis (Section 12.3.3.1.1).

#### 12.3.3.3.2 Analysis of Key Secondary Variables

The following key secondary efficacy and pharmacodynamic variables will be analyzed during the IA using an Analysis of Covariance (ANCOVA) model and nominal *P* value will be provided for descriptive purpose:

1. Absolute change in SwCl from baseline at Week 4
2. Absolute change in CFQ-R respiratory domain score from baseline at Week 4

The model will use the change from baseline value at Week 4 as the dependent variable and include treatment group as fixed effects with continuous baseline ppFEV1, age at screening (<18 versus ≥18 years of age), and sex (male versus female) as covariates.

Additional details will be provided in the SAP.

#### 12.3.3.4 Multiplicity Adjustment

The Lan and DeMets alpha spending function will be applied to the primary endpoint of the absolute change in ppFEV1 at Week 4 to control the overall type I error rate of 0.05 such that an alpha of 0.01 will be preserved for the final analysis.

If the number of subjects included in the IA is 140, the primary endpoint of the absolute change from baseline in ppFEV1 at Week 4 will be tested at an alpha of 0.044 during the IA. The actual alpha at the IA ( $\alpha_0$ ) will be determined based on the actual number of subjects included in the IA. If the study does not cross the efficacy boundary during the IA (*P* value  $\geq \alpha_0$ ), then the primary endpoint will be tested at an alpha of 0.01 at the final analysis when all subjects complete study participation.

The key secondary endpoints will be formally tested at an alpha of 0.05 at the final analysis when all subjects complete study participation only if the primary endpoint is statistically significant at the IA or at the final analysis. A hierarchical testing procedure will be used to control the type I error rate for the multiple key secondary endpoints tested at an alpha of 0.05. For a test at any step to be considered statistically significant within the testing hierarchy, it must be statistically significant, and all previous tests (if any) within the hierarchy must be statistically significant at the 0.05 level. The testing order of the key secondary endpoints is as follows:

1. First key secondary endpoint: Absolute change in ppFEV1 from baseline through Week 24
2. Second key secondary endpoint: Number of PEx through Week 24

3. Third key secondary endpoint: Absolute change in SwCl from baseline through Week 24
4. Fourth key secondary endpoint: Absolute change in CFQ-R respiratory domain from baseline through Week 24
5. Fifth key secondary endpoint: Absolute change in BMI from baseline at Week 24
6. Sixth key secondary endpoint: Absolute change in SwCl from baseline at Week 4
7. Seventh key secondary endpoint: Absolute change in CFQ-R respiratory domain score from baseline at Week 4

### 12.3.4 Safety Analysis

All safety analyses will be based on data from the TE Period for all subjects in the Safety Set.

The overall safety profile of study drug will be assessed based on the following safety and tolerability endpoints:

- Treatment-emergent adverse events (TEAEs)
- Clinical laboratory values (i.e., hematology, serum chemistry, coagulation, and urinalysis)
- ECGs
- Vital signs
- Pulse oximetry

All safety data from the TE Period will be summarized by treatment group.

All safety data will be presented in individual subject data listings.

#### 12.3.4.1 Adverse Events

For analysis purposes, AEs will be classified as pretreatment AEs, TEAEs, or post-treatment AEs, defined as follows:

- **Pretreatment AE:** any AE that occurred before the first dose date of study drug
- **TEAE:** any AE that worsened (either in severity or seriousness) or that was newly developed at or after the first dose date of study drug through the end of the TE Period
- **Post-treatment AE:** any AE that worsened (either in severity or seriousness) or that was newly developed after the TE Period

For AEs with missing or partial start dates, if there is no clear evidence that the AEs started before or after study drug treatment, then the AEs will be classified as TEAEs.

AE summary tables will be presented for TEAEs only, overall and by treatment group, and will include the following:

- All TEAEs
- TEAEs by strongest relationship
- TEAEs by maximum severity
- TEAEs leading to treatment discontinuation

- TEAEs leading to treatment interruption
- Serious TEAEs
- TEAEs leading to death
- Grade 3 and Grade 4 TEAEs
- Frequently reported TEAEs

Summaries will be presented by MedDRA SOC and PT using frequency counts and percentages (i.e., number and percentage of subjects with an event). When summarizing the number and percentage of subjects with an event, subjects with multiple occurrences of the same AE or a continuing AE will be counted once, only the maximum severity level will be presented in the severity summaries, and the strongest relationship level in the relationship summaries.

In addition, a listing containing individual subject level AE data for all deaths and other serious and significant AEs will be provided separately. All AEs, including pre- and post-treatment AEs, will be presented in individual subject data listings.

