##### **11.6.4.2 Hospitalization for CF**

Subjects will be queried about planned and unplanned hospitalizations lasting  $\geq 24$  hours that occurred during the study. The dates of hospitalizations and the reasons for hospitalizations will be documented.

For any hospitalization (planned and unplanned), the procedures for safety reporting should also be followed.

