### Power for Selected Key Secondary Endpoints

A key secondary endpoint is the absolute change in ppFEV1 from baseline through Week 24. Assuming a within-group SD of 7 percentage points and a 10% dropout rate at Week 24, a sample size of 180 subjects in each treatment group will have approximately 99% power to detect a difference between the treatment groups of 5.0 percentage points for the absolute change in ppFEV1 from baseline through Week 24, based on a 2-sided, 2-sample *t*-test at a significance level of 0.05.

Another key secondary endpoint is the number of PEx through Week 24. Assuming a rate of PEx for the placebo group of 0.6 over 24 weeks and a 10% dropout rate, with 180 subjects and the overdispersion parameter of 0.5 in each treatment group, the power to detect a 40% reduction in the PEx rate for TC group compared to placebo group is approximately 80%, based on a 2-sided, 2-sample negative binomial regression model test for the ratio of rates, at a significance level of 0.05.

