## **13 PROCEDURAL, ETHICAL, REGULATORY, AND ADMINISTRATIVE CONSIDERATIONS**

### **13.1 Adverse Event and Serious Adverse Event Documentation, Severity Grading, and Reporting**

#### **13.1.1 Adverse Events**

##### **13.1.1.1 Definition of an Adverse Event**

An AE is defined as any untoward medical occurrence in a subject during the study; the event does not necessarily have a causal relationship with the treatment. This includes any newly occurring event or worsening of a pre-existing condition (e.g., increase in its severity or frequency) after the ICF is signed.

An AE is considered serious if it meets the definition in [Section 13.1.2.1](#).

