**13.1.2 Serious Adverse Events****13.1.2.1 Definition of a Serious Adverse Event**

An SAE is any AE that meets any of the following outcomes:

- Fatal (death, regardless of cause, that occurs during participation in the study or occurs after participation in the study and is suspected of being a delayed toxicity due to administration of the study drug)
- Life-threatening, such that the subject was at immediate risk of death from the reaction as it occurred
- Inpatient hospitalization or prolongation of hospitalization
- Persistent or significant disability/incapacity (disability is defined as a substantial disruption of a person’s ability to conduct normal life functions)
- Congenital anomaly or birth defect

- Important medical event that, based upon appropriate medical judgment, may jeopardize the subject or may require medical or surgical intervention to prevent 1 of the outcomes listed above (e.g., an allergic bronchospasm requiring intensive treatment in an emergency room or at home)

If a subject has a hospitalization or procedure (e.g., surgery) for an event or condition that occurred before the subject signed the ICF, and the hospitalization or procedure was planned before the subject signed the ICF, the hospitalization or procedure will not be considered to indicate an SAE, unless an AE caused the hospitalization or procedure to be rescheduled sooner or to be prolonged relative to what was planned. In addition, hospitalizations clearly not associated with an AE (e.g., social hospitalization for purposes of respite care) will not be considered to indicate an SAE.

Clarification will be made between the terms “serious” and “severe” because they are not synonymous. The term “severe” is often used to describe the intensity (severity) of a specific event, as in mild, moderate, or severe myocardial infarction. The event itself, however, may be of relatively minor medical significance, such as a severe headache. This is not the same as “serious,” which is based on subject/event outcome or action described above, and is usually associated with events that pose a threat to a subject’s life or functioning. Seriousness, not severity, serves as a guide for defining expedited regulatory reporting obligations.

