#### **9.4.1 Adverse Events**

For analysis purposes, AEs will be classified as pretreatment AEs, TEAEs, or post-treatment AEs, defined as follows:

**Pretreatment AE:** any AE that occurred before the first dose date of study drug

**TEAE:** any AE that worsened (either in severity or seriousness) or that was newly developed on or after the first dose date of study drug through the end of the TE period

**Post-treatment AE:** any AE that worsened (either in severity or seriousness) or that was newly developed after the TE period

For AEs with completely missing or partially missing start dates, if there is no clear evidence that the AEs started before or after study treatment, the AEs will be classified as TEAEs.

Details for imputing missing or partial start dates of adverse events are described in [Appendix E](#).

An overview of all TEAEs by treatment group and overall will be summarized in the following categories:

- Number of TEAEs (total number of TEAEs only)
- Subjects with any TEAEs
- Subjects with TEAEs by strongest relationship
- Subjects with TEAEs by maximum severity
- Subjects with TEAEs leading to study drug discontinuation (discontinuation of any study drug)
- Subjects with TEAEs leading to study drug interruption (interruption of any study drug)
- Subjects with Grade 3/4 TEAEs
- Subjects with related TEAEs
- Subjects with serious TEAEs
- Subjects with related serious TEAEs
- Subjects with TEAE leading to death

The following summary tables of TEAEs will be presented by treatment group:

- All TEAEs
- Grade 3/4 TEAEs
- TEAEs by strongest relationship
- TEAEs by maximum severity
- TEAEs leading to treatment discontinuation

- TEAEs leading to treatment interruption
- Related TEAEs
- Serious TEAEs
- Related serious TEAEs
- TEAEs leading to death

Summaries will be presented by MedDRA SOC and PT using frequency counts and percentages (i.e., number and percentage of subjects with an event). When summarizing the number and percentages of subjects, subjects with multiple occurrences of the same adverse event or a continuing adverse event will be counted once, and only the maximum severity level will be presented in the severity summaries, and the strongest relationship level in the relationship summaries.

Additional summary tables will be presented by treatment for TEAEs showing number and percentage of subjects

- All TEAEs by PT

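### The by-arm count of subjects with serious adverse events includes hospitalised pulmonary exacerbations, an efficacy outcome, so it can partly offset an excess of other serious events on active drug; a row without them would be a cheap addition

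*Protocol*

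**What the plan says.** Protocol Section 13.1.1.1 defines adverse events broadly: "An AE is defined as any untoward medical occurrence in a subject during the study", and "This includes any newly occurring event or worsening of a pre-existing condition". Section 13.1.2.1 makes an event serious on "Inpatient hospitalization or prolongation of hospitalization". Of certain admissions planned before consent it says "the hospitalization or procedure will not be considered to indicate an SAE", and it also sets aside admissions clearly unrelated to an adverse event. PEx is not exempted. Section 11.6.4.2 adds: "For any hospitalization (planned and unplanned), the procedures for safety reporting should also be followed".

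PEx is also an efficacy outcome. Section 11.6.4.1 defines it as new or changed antibiotics for at least four listed signs or symptoms, and Section 12.3.3.4 places the number of PEx second in the key secondary hierarchy.

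For reporting, Protocol Section 12.3.4.1 states that "AE summary tables will be presented for TEAEs only, overall and by treatment group". The overview in SAP Section 9.4.1 has by-arm rows for any, Grade 3/4 and serious events, the last being "Subjects with serious TEAEs". SAP Section 10.1.4 reuses these analyses at the interim. SAP Section 9.4 makes safety descriptive only. None of the visible rows excludes PEx.

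**The concern.** A by-arm total of subjects with a serious event is normally read as a measure of harm. Here it combines two things: hospitalised PEx, which the drug is expected to reduce, and all other serious events, which it might increase. The first pulls the active-arm figure down and can cancel some of a rise in the second. With no formal safety testing, readers compare the percentages directly, so two similar totals could be taken as reassurance that they do not give.

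The preferred-term rows do not solve this by subtraction. They count subjects, and one subject can have both a hospitalised PEx and another serious event. Harm spread thinly over many terms is what a total is best placed to show.

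**Working it through.** **Inputs from the documents** (Protocol Section 12.1, SAP Section 7.2): "Assuming a rate of PEx for the placebo group of 0.6 over 24 weeks"; a 40% reduction, so 0.6 × 0.6 = 0.36 on active; overdispersion k = 0.5; 180 per arm; 10% dropout; two-sided 0.05.

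**Assumptions, not in the documents:** the share h of PEx that are hospitalised (10 to 50%); the proportion q of subjects with a non-PEx event; independence of the two kinds of event.

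**1. Reproduce the plan's power.** With n = 180 × 0.9 = 162 per arm, the variance of the log rate ratio is (1/162)(1/0.6 + 1/0.36 + 2 × 0.5) = 0.0336, so SE = 0.183. Then 0.511/0.183 = 2.79, and the power is Φ(2.79 − 1.96) = 79.6%, against about 80% stated. The inputs are read as intended.

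**2. Subjects with at least one PEx over 24 weeks.** P = 1 − (1 + kμ)^(−1/k).
- Placebo: 1 − 1.30^(−2) = 40.8%, about 73 of 180.
- Active: 1 − 1.18^(−2) = 28.2%, about 51 of 180.
- Gap: 12.6 points.

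**3. Serious PEx and the break-even.** Replace μ by hμ and keep k. The total is 1 − (1 − q)(1 − p), where p is the risk of a serious PEx. The two totals are equal when q_active = 1 − (1 − q_placebo)(1 − p_placebo)/(1 − p_active).

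| Share hospitalised | Serious PEx, placebo | Serious PEx, active | Break-even on active, q_placebo = 3% | Break-even on active, q_placebo = 5% |
|---|---|---|---|---|
| 10% | 5.7% | 3.5% | 5.2% | 7.2% |
| 20% | 11.0% | 6.8% | 7.3% | 9.3% |
| 30% | 15.8% | 10.0% | 9.3% | 11.2% |
| 50% | 24.4% | 15.8% | 12.9% | 14.7% |

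**4. Two illustrations at 30% hospitalised.**
- Equal non-PEx risk of 5% in both arms: the totals read 20.0% placebo and 14.5% active. That gap is efficacy only.
- Non-PEx risk of 3% placebo and 8% active: 1 − 0.842 × 0.97 = 18.4% and 1 − 0.900 × 0.92 = 17.2%. The other serious events are 2.7 times as common on active, yet the total is slightly lower there.

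**5. Interim.** The trigger is 140 subjects past Week 4 and 100 past Week 12. Take PEx as proportional to time, 30% hospitalised and q_placebo = 3%.
- At 12 weeks, serious PEx affect 8.4% vs 5.2%, and the break-even is 6.3%.
- At 4 weeks, they affect 2.9% vs 1.8%, and the break-even is 4.1%.

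**6. Row for any event.** All PEx count here.
- If 90% of subjects in each arm have another event, the row reads 94.1% vs 92.8%, a gap of 1.3 points. It could hide a 1.8-point excess.
- At 70% it reads 82.2% vs 78.5%, a gap of 3.8 points. It could hide a 5.3-point excess.

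**7. Grade 3/4 row.** The documents give no share of PEx graded 3 or higher, so no figure can be put on it.

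**The case against.** The strongest reply is that counting every event is complete reporting, contradicts nothing in the plan, and is not the only view of safety.
- SAP Section 9.4.1 splits the serious and Grade 3/4 tables by organ class and preferred term, so PEx should be visible. It also has related and related-serious rows, which should remove many disease-driven PEx.
- The same section plans a separate subject-level listing that includes serious and Grade 3/4 events. With the treatment codes, the missing count could be built from it. In the 3% vs 8% illustration that is about 5 vs 14 of 180 subjects, which an attentive reader could notice.
- SAP Section 5.2.1, on clinical event counts, analyses unplanned hospitalizations for reasons other than antibiotic therapy.
- The SAP contents show a redacted entry directly after Section 9.4.1, which may hold a further analysis.

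All of this stands as partial mitigation. It does not close the gap. Related rows depend on investigator attribution, the listing requires an unplanned recount, and the hospitalization analysis omits events that are serious for other reasons. No visible output gives the all-cause, by-arm count of subjects with a non-PEx serious event.

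A reader might also infer that the headline rows will favour active drug whatever harm it causes. The documents do not support that. Beyond the break-even the serious total is higher on active, and both the hospitalised share and the other event rates are assumed.

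**Conclusion.** The point holds for the visible totals, chiefly the count of subjects with serious events. The direction follows from the protocol's definitions and the assumed PEx reduction. The size rests on assumptions: with 20 to 50% of PEx hospitalised, 3% of placebo subjects with another serious event and independence, the active rate could reach about 7 to 13% over 24 weeks before the totals are equal. The interim figures are smaller. The row for any event is little affected if most subjects have another event, and the effect on Grade 3/4 is unknown.

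Two stronger readings should be resisted. One is that harm would be hidden from the whole safety package; the outputs listed above, and the possible content of the redacted entry, argue against it. The other is that the monitoring committee or the final report judges safety from these totals alone. Protocol Section 12.3.4 also lists laboratory values, ECGs, vital signs and oximetry, and the committee's review is governed by a charter and a separate analysis plan that are not among the documents. This is a cheap improvement, not a defect that undermines the safety analysis.

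**What to change.** In SAP Section 9.4.1, and through Section 10.1.4 for the interim, keep all planned rows. Add two by-arm rows: subjects with serious TEAEs excluding PEx, and subjects with Grade 3/4 TEAEs excluding PEx. Identify PEx by a preferred-term list fixed by blinded staff before the interim data lock, by which time SAP Section 4 already requires the SAP to be final.

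The cost is a short SAP addition, the list, and two rows at each analysis. Conduct, dosing and alpha are unchanged. The downside is dependence on the list: a true respiratory harm coded as PEx would drop out, and a PEx recorded only as separate symptoms would stay in. The new rows should therefore stand beside the all-event rows and not replace them.
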